9.2.5 SAEs (Including Deaths) and Adverse Events Leading to Study Drug Discontinuation

SAEs (including deaths) and AEs leading to study drug discontinuation will be summarized by SOC and PT and in listing format.

9.2.6 Adverse Events of Special Interest

The AESI categories will be identified by the search criteria per Standard MedDRA Queries (SMQs)/Company MedDRA Queries (CMQs) specified in [Appendix B](#).

Treatment-emergent Adverse events of special interest will be summarized by SOC and PT and listing format. Additionally, AESI rates per 100 patient years of exposure will be provided for each AESI category ([Appendix B](#)) in the AE overview summary.

9.3 Analysis of Laboratory Data

Data collected from central and local laboratories, including additional laboratory testing due to an SAE, will be used in all analyses, except for Baseline where SAE-related laboratory assessments on or before the first dose of study drug will be excluded. The clinical laboratory tests defined in the protocol (e.g., hematology and clinical chemistry) will be summarized.

Analysis of Quantitative Laboratory Parameters

Each laboratory variable will be summarized for all time points with the number of non-missing observations, mean and standard deviation, median, minimum and maximum. Mean change from Maintenance Baseline to each applicable post-baseline visit will be summarized for selected laboratory variables, with the number of observations, baseline mean, and visit mean. The change from Maintenance Baseline mean, standard error, and 95% confidence interval will be presented within each treatment group.

Treatment group differences between upadacitinib treatment group and placebo group for changes from Maintenance Baseline will be analyzed using a one-way Analysis of Variance (ANOVA) model with treatment as a fixed factor and 95% CI for treatment difference will be presented for selected laboratory parameters, for SA_A and SA_C population only.

Shift Table Analyses

Changes in laboratory parameters will be tabulated using shift tables categorized as low, normal, or high based on the normal ranges of the laboratory used for each sample. A shift table from Baseline to minimum and maximum value (based on normal range) will

be created. A similar shift table will be provided to summarize shifts from Baseline to the final post-baseline value.

Potentially Clinically Significant Laboratory Values

The criteria for potentially clinically significant laboratory values will be determined by CTCAE criteria of Grade 3, Grade 4 and \geq Grade 3, with a grade worsening compared to baseline. Toxicity grading scale is based on National Cancer Institute Common Toxicity Criteria (NCI CTC) AE version 4.03. The number and percentage of subjects meeting the criteria for potentially clinically significant laboratory values will be summarized by treatment group. Listings will be provided to summarize subject-level laboratory data for subjects meeting the criteria.

Assessment of Liver Enzyme and Bilirubin Elevations

The liver-specific laboratory tests include the serum glutamic pyruvic transaminase (SGPT/ALT), serum glutamic-oxaloacetic transaminase (SGOT/AST), alkaline phosphatase (ALP), and total bilirubin (TBL). The frequencies and percentages of subjects with post baseline liver specific function test values that meet the following criteria of potential clinical interest will be summarized by treatment group:

- $ALT \geq 3 \times ULN$
- $ALT \geq 5 \times ULN$
- $ALT \geq 10 \times ULN$
- $ALT \geq 20 \times ULN$
- $AST \geq 3 \times ULN$
- $AST \geq 5 \times ULN$
- $AST \geq 10 \times ULN$
- $AST \geq 20 \times ULN$
- $TBL \geq 2 \times ULN$
- $ALP \geq 1.5 \times ULN$
- $ALT \text{ and/or } AST \geq 3 \times ULN \text{ and } TBL \geq 1.5 \times ULN$

- ALT and/or AST $\geq 3 \times$ ULN and TBL $\geq 2 \times$ ULN,

where ULN is the upper normal limit. The maximum ratio relative to the ULN will be used to determine if subjects meet any of the criteria listed above.

A listing of potentially clinically significant liver function laboratory values will be provided. The listing will include all subjects who met any of the following 4 criteria:

- ALT $\geq 2.5 \times$ ULN, or
- AST $\geq 2.5 \times$ ULN, or
- ALP $\geq 1.5 \times$ ULN, or
- TBL $\geq 1.5 \times$ ULN.

In addition, eDISH plots will be created displaying post-baseline total bilirubin versus post-baseline ALT, in terms of the maximum ratio relative to the ULN (not necessarily concurrent).

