8.1.8.3 Analysis of Laboratory and Vital Sign Data

Changes from Baseline in continuous laboratory and vital sign parameters will be summarized by treatment group. Treatment group differences between each of the upadacitinib dosing groups and the placebo group for mean changes from Baseline will be analyzed using ANOVA.

Vital signs and laboratory data will be described by statistical characteristics and frequency of abnormal values. Frequencies and percentages of subjects with laboratory shifts from Baseline to the final values using normal ranges to define categories (low, normal, high, and missing) will be summarized by the respective categories. Values beyond the normal values will be listed. Low or high laboratory values will also be flagged in the data listings. Analysis details will be specified in the SAP.

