3.0 Endpoints

The induction baseline (thereafter referred to as Baseline) visit date is the date when the first dose of study drug is received during Induction Studies. The baseline value for a variable is defined as the last non-missing value on or before the date of the first dose of study drug during Induction Studies.

The maintenance baseline visit date is on the same day as the final visit in the Induction Studies (thereafter referred to as Maintenance Baseline). The maintenance baseline value for a variable is defined as the last non-missing value on or before the date of the first dose of study drug during Maintenance Study.

The terminologies and efficacy variables are defined as below:

- Mayo Score
 - **Full Mayo Score:** composite score of UC disease activity based on the stool frequency subscore [SFS] (0 – 3), rectal bleeding subscore [RBS] (0 – 3), physician's global assessment [PGA] subscore (0 – 3) and endoscopic subscore (0 – 3). This score ranges from 0 – 12 points with higher scores representing more severe disease.
 - **Partial Mayo Score:** Full Mayo score minus the endoscopic subscore.
 - **Adapted Mayo Score:** Full Mayo score minus the PGA subscore.
 - **Partial Adapted Mayo Score:** Adapted Mayo score minus the endoscopic subscore.
- Clinical Remission
 - **per Full Mayo Score:** Full Mayo score ≤ 2 with no subscore > 1 .
 - **per Adapted Mayo Score:** Adapted Mayo score ≤ 2 , with SFS ≤ 1 and not greater than baseline, RBS of 0, and endoscopic subscore ≤ 1 .
 - **per Partial Mayo Score:** Partial Mayo score ≤ 2 , with no subscore > 1 .
- Clinical Response
 - **per Full Mayo Score:** decrease in Full Mayo score of ≥ 3 points and $\geq 30\%$ from Baseline, PLUS a decrease in RBS ≥ 1 or an absolute RBS ≤ 1 .
 - **per Adapted Mayo Score:** decrease in Adapted Mayo score ≥ 2 points and $\geq 30\%$ from Baseline, PLUS a decrease in RBS ≥ 1 or an absolute RBS ≤ 1 .
 - **per Partial Mayo Score:** decrease in Partial Mayo score ≥ 2 points and $\geq 30\%$ from Baseline, PLUS a decrease in RBS ≥ 1 or an absolute RBS ≤ 1 .

- **per Partial Adapted Mayo Score:** decrease in Partial Adapted Mayo score ≥ 1 point and $\geq 30\%$ from Baseline, PLUS a decrease in RBS ≥ 1 or an absolute RBS ≤ 1 .
- **Endoscopic Improvement:** Endoscopic subscore of 0 or 1.
- **Endoscopic Remission:** Endoscopic subscore of 0.
- **Histologic Improvement:** decrease from Baseline in Geboes score.
- **Histologic Remission:** Geboes score < 2 .

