8.0 Efficacy Analyses

8.1 General Considerations

The primary and secondary efficacy endpoints will be analyzed based on ITT_A population as defined in Section 4.0. The primary and ranked secondary efficacy endpoints as specified in Section 3.1 and Section 3.2 will be tested with graphical multiplicity adjustment to ensure a strong control of family-wise type I error rate at significance level $\alpha=0.05$ (2-sided).

For analyses based on ITT_A population, unless otherwise specified, categorical variables will be analyzed using Cochran-Mantel-Haenszel (CMH) test, stratified by Bio-IR status (Bio-IR or Non-Bio-IR) at the Baseline of Induction Study, clinical remission status at Week 0 (yes or no), and corticosteroid use at Week 0 (yes or no). Any subject who was randomized under the wrong stratum will be analyzed according to the actual stratum the subject belongs to. Continuous variables collected longitudinally will be analyzed using Mixed-Effect Model Repeat Measurement (MMRM) model. Continuous variables collected at only one post-baseline visit will be analyzed using an Analysis of Covariance (ANCOVA) model. MMRM model includes the categorical fixed effects of treatment, visit and treatment-by-visit interaction, randomization stratification factors (Bio-IR status (Bio-IR or Non-Bio-IR) at the Baseline of the Induction Study, clinical remission status at

Week 0 (yes or no), and corticosteroid use at Week 0 (yes or no)), and the continuous fixed covariates of Baseline measurements. An unstructured variance covariance matrix (UN) will be used. If the model cannot converge, autoregressive (1) covariance structure matrix will be used. The parameter estimations are based on the method of restrictive maximum likelihood (REML). The fixed effects will be used to report model-based means at corresponding visits. ANCOVA model includes the categorical fixed effects of treatment, randomization stratification factors (Bio-IR status: Bio-IR or Non-Bio-IR) at the Baseline of the Induction Study, clinical remission status at Week 0 (yes or no), and corticosteroid use at Week 0 (yes or no)), and the continuous fixed covariates of Baseline measurements.

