9.4 Analysis of Vital Signs

Vital sign measurements of systolic and diastolic blood pressure, pulse rate, body weight, respiratory rate and body temperature will be summarized.

Each vital sign variable will be summarized for all time points with the number of non-missing observations, mean and standard deviation, median, minimum and maximum. Mean change from Maintenance Baseline to each applicable post-baseline visit will be summarized for each vital sign variable, with the number of observations, Baseline mean, and visit mean. The change from Maintenance Baseline mean, standard error, and 95% confidence interval will be presented within each treatment group.

Treatment group differences between upadacitinib treatment group and placebo group for changes from Maintenance Baseline will be analyzed using a one-way Analysis of Variance (ANOVA) with treatment as a fixed factor and 95% CI for treatment difference will be presented for each vital sign variable, for SA_A and SA_C population only.

Vital sign variables will be evaluated based on potentially clinically significant (PCS) criteria ([Appendix C](#)). For each vital sign PCI criterion, the number and percentage of subjects who have a vital sign value meeting the criteria will be summarized. Listings will be provided to summarize subject-level vital sign data for subjects meeting PCI criteria.

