9.3 Analysis of Laboratory Data

Data collected from central and local laboratories, including additional laboratory testing due to an SAE, will be used in all analyses, except for Baseline where SAE-related laboratory assessments on or before the first dose of study drug will be excluded. The clinical laboratory tests defined in the protocol (e.g., hematology and clinical chemistry) will be summarized.

Analysis of Quantitative Laboratory Parameters

Each laboratory variable will be summarized for all time points (starting with Baseline) with the number of non-missing observations, mean and standard deviation, median, minimum and maximum. Mean change from Baseline to each applicable post-baseline visit will be summarized for selected laboratory variables, with the number of observations, baseline mean, and visit mean. The change from baseline mean, standard error, and 95% confidence interval will be presented for the mean change from Baseline within each treatment group.

For SA1 population, treatment group differences between upadacitinib treatment group and placebo group for changes from Baseline will be analyzed using a one-way Analysis of Variance (ANOVA) model with treatment as a fixed factor and 95% CI for treatment difference will be presented for selected laboratory parameters.

Shift Table Analyses

Changes in laboratory parameters will be tabulated using shift tables categorized as low, normal, or high based on the normal ranges of the laboratory used for each sample. A shift table from Baseline to minimum and maximum value (based on normal range) will be created. A similar shift table will be provided to summarize shifts from Baseline to the final post-baseline value.

Potentially Clinically Significant Laboratory Values

The criteria for potentially clinically significant laboratory values will be determined by CTCAE criteria of Grade 3, Grade 4 and \geq Grade 3, with a grade worsening compared to baseline. Toxicity grading scale is based on National Cancer Institute Common Toxicity Criteria (NCI CTC) AE version 4.03. The number and percentage of subjects meeting the criteria for potentially clinically significant laboratory values will be summarized by treatment group. Listings will be provided to summarize subject-level laboratory data for subjects meeting the criteria.

Assessment of Liver Elevations

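### Laboratory and vital-sign changes are compared with placebo by treatment-only ANOVA, which fixes the baseline slope at 1; estimating that slope would give intervals at least as narrow for almost no cost

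*SAP*

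**What the plan says.** Substudy 3 SAP, 9.3: differences between upadacitinib and placebo "for changes from Maintenance Baseline will be analyzed using a one-way Analysis of Variance (ANOVA) model with treatment as a fixed factor", and a "95% CI for treatment difference will be presented for selected laboratory parameters, for SA_A and SA_C population only". Section 9.4 repeats the model for vital signs ("for changes from Maintenance Baseline will be analyzed using a one-way Analysis of Variance (ANOVA) with treatment as a fixed factor"), with an interval for each vital sign in the same two populations.

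Substudy 2 SAP, 9.3: in the Part 1 safety population, "changes from Baseline will be analyzed using a one-way Analysis of Variance (ANOVA) model with treatment as a fixed factor", again with intervals for selected laboratory parameters. Section 9.4 does the same for each vital sign.

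Protocol 8.1.8.3 says that differences between each dose group and "the placebo group for mean changes from Baseline will be analyzed using ANOVA". Protocol 8.1.8.1 also names a one-way ANOVA for laboratory changes and says that vital signs are handled similarly.

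The baseline value is available. Substudy 3 SAP 3.0 defines it for every variable: "The maintenance baseline value for a variable is defined as the last non-missing value on or before the date of the first dose" of maintenance study drug. Section 8.1 of the same SAP already uses a covariate of this kind for continuous efficacy endpoints, where the MMRM and ANCOVA models hold treatment, the stratification factors "and the continuous fixed covariates of Baseline measurements". None of the safety sections cited here plans a baseline-adjusted comparison, even as a sensitivity analysis.

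**The concern.** A one-way ANOVA on change assumes that a subject who starts one unit higher than another will, on the same treatment, also be one unit higher at the visit. Where values regress towards the mean, or where a raised value after induction settles, the slope of the visit value on baseline is below 1. The subtraction then leaves variation in the error term that the recorded baseline could explain.

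At stake is the precision of the placebo-controlled estimates of mean change. Protocol 3.0 and 3.2 describe effects of this drug or its class on hemoglobin, white cells, lymphocytes, creatinine, lipids, transaminases and CPK, so a tighter interval is useful where one of these is among the selected parameters.

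**Working it through.** **The plan's own figure.** The plan states no width, precision or power for these comparisons, so there is none to reproduce. The arm size used below, 150, comes from Substudy 3 SAP 2.4. The power claim in that section (above 95% for 12% against 40%, two-sided Fisher's exact test at 0.025) reproduces at 0.9997 by full enumeration, but it has no bearing on this point.

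**Inputs.** From the documents: three Cohort 1 arms of 150, a treatment-only model on change, and a 95% interval. Not in the documents: the SD at baseline (s0), the SD at the visit (s1), and the correlation between the two values (r). I assume r from 0.3 to 0.9, first with s0 = s1 and then with s1/s0 from 0.8 to 1.5. I also assume one three-arm model and a common slope across arms.

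**Formulas.** Per-subject variance behind the treatment difference:

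- ANOVA on change: s0² + s1² − 2·r·s0·s1
- ANCOVA with baseline: s1²·(1 − r²)
- ANOVA minus ANCOVA: s0² − 2·r·s0·s1 + r²·s1² = (s0 − r·s1)²

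The last line is never negative. It is zero only when r·s1/s0 = 1, that is, when the slope of the visit value on baseline is exactly 1.

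**Equal SDs.** The variance ratio is (1 − r²) / [2(1 − r)] = (1 + r)/2, so the width ratio ANCOVA/ANOVA is √[(1 + r)/2]. The half-width in SD units is t × √(variance) × √(2/150), with 447 degrees of freedom for ANOVA and 446 for ANCOVA. The ANCOVA half-width also carries a small allowance for chance baseline imbalance.

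| r | Width ratio | ANOVA half-width | ANCOVA half-width | Narrower by |
|---|---|---|---|---|
| 0.3 | 0.806 | 0.269 | 0.217 | 19.4% |
| 0.5 | 0.866 | 0.227 | 0.197 | 13.4% |
| 0.7 | 0.922 | 0.176 | 0.162 | 7.8% |
| 0.8 | 0.949 | 0.144 | 0.136 | 5.1% |
| 0.9 | 0.975 | 0.101 | 0.099 | 2.5% |

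The half-widths assume that all 150 subjects per arm have a value at the visit. Fewer would widen both columns and leave the ratio essentially unchanged.

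**Unequal SDs.** Over s1/s0 from 0.8 to 1.5 and r from 0.3 to 0.9, the width ratio runs from 0.71 (s1/s0 = 0.8, r = 0.3) to 1.00 (s1/s0 = 1.25, r = 0.8). In the second case the slope is 0.8 × 1.25 = 1, so nothing is gained.

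**Simulation.** With three arms of 150 and 3,000 runs at each of r = 0.3, 0.5, 0.7 and 0.9, the mean width ratios were 0.807, 0.867, 0.923 and 0.976. ANCOVA was narrower in every run at the first three values and in 99.9% of runs at r = 0.9. Coverage was 94.7% to 95.2% for ANOVA and 94.2% to 95.5% for ANCOVA.

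**The case against.** The strongest reply is that this is a modelling preference. A treatment-only ANOVA on change is a legitimate, pre-specified analysis that follows the protocol. It is unbiased across randomisations, with nominal coverage. The SAP sections attach no decision rule to these mean differences. Individual laboratory safety is judged from shift tables, CTCAE Grade 3 and 4 counts, liver thresholds and vital-sign criteria, none of which would move. The efficacy ANCOVA serves alpha-controlled endpoints, so its use there does not make the safety model an inconsistency. All of this stands, and it keeps the point minor. It does not remove the gain: the covariate is recorded and costs one degree of freedom.

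A reader might infer more than the documents support:

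- **That baseline is ignored, or that the intervals are invalid.** Baseline is subtracted; only the freedom of its slope is missing. Coverage is about 95%.
- **That every laboratory variable is affected.** Both SAPs limit the laboratory intervals to selected parameters and do not name them in these sections. Substudy 3 limits them further to two populations. Only the vital signs are covered in full. Neutrophils are not among the laboratory effects described in protocol 3.0 and 3.2; neutropenia appears in 6.1.1.3 as an event of special interest.
- **That these are strictly randomised estimates.** Both SAPs group the safety populations as treated, by the most frequent regimen received.
- **That the fix is worth a third more subjects.** That figure is 1/0.75 = 1.33 at r = 0.5 alone. No correlation is documented, and these summaries have no power target.

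**Conclusion.** The point holds as a loss of precision. For selected laboratory parameters and each vital sign in Substudies 2 and 3, the planned interval is in expectation no narrower than the ANCOVA interval, given a common slope and apart from one degree of freedom. The common-slope condition matters more in Substudy 2, where allocation is 2:1. If slopes differ between arms of unequal size, the never-wider result is not guaranteed.

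The size cannot be derived from the documents. With equal SDs it is about 19% of the width at r = 0.3, falling to 2.5% at r = 0.9. It is close to zero for any parameter whose slope on baseline is near 1. No safety conclusion has been shown to turn on a difference of this size.

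**What to change.** - **Substudy 3 SAP 9.3 and 9.4:** replace the one-way ANOVA by ANCOVA with treatment and the Maintenance Baseline value of the same parameter. Report adjusted differences from placebo with 95% confidence intervals in SA_A and SA_C. The covariate should be the Maintenance Baseline because the change is measured from it; the efficacy models in that SAP use the induction Baseline.
- **Substudy 2 SAP 9.3 and 9.4:** make the same change with that substudy's Baseline, but only if the analysis has not been done. The protocol synopsis says that all subjects have completed induction, SAP 2.3 has the sponsor unblinded at the induction lock, and no lock date is given. If the analysis is done, add ANCOVA as a labelled supplementary analysis.
- **Protocol 8.1.8.1 and 8.1.8.3:** align the ANOVA wording, or record the departure in each SAP's version history. The second route is lighter and has a precedent: version 4.0 of the Substudy 3 SAP replaced the protocol's MMRM in this way as the primary missing-data approach for continuous endpoints.

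The cost is one model term in existing safety programs, one degree of freedom and a line of documentation. No new data are needed.

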9.4 Analysis of Vital Signs

Vital sign measurements of systolic and diastolic blood pressure, pulse rate, body weight, respiratory rate and body temperature will be summarized.

Each vital sign variable will be summarized for all time points with the number of non-missing observations, mean and standard deviation, median, minimum and maximum. Mean change from Maintenance Baseline to each applicable post-baseline visit will be summarized for each vital sign variable, with the number of observations, Baseline mean, and visit mean. The change from Maintenance Baseline mean, standard error, and 95% confidence interval will be presented within each treatment group.

Treatment group differences between upadacitinib treatment group and placebo group for changes from Maintenance Baseline will be analyzed using a one-way Analysis of Variance (ANOVA) with treatment as a fixed factor and 95% CI for treatment difference will be presented for each vital sign variable, for SA_A and SA_C population only.

Vital sign variables will be evaluated based on potentially clinically significant (PCS) criteria ([Appendix C](#)). For each vital sign PCI criterion, the number and percentage of subjects who have a vital sign value meeting the criteria will be summarized. Listings will be provided to summarize subject-level vital sign data for subjects meeting PCI criteria.

